Study BN40423 was originally designed (under Protocol Versions 1-3) to include three dosing regimens under a blinded monthly dosing paradigm: RO7234292 every 4 weeks (Q4W), RO7234292 every 8 weeks (Q8W) (with alternating placebo), and placebo Q4W. The Sponsor decided to stop enrollment under this original protocol containing this blinded monthly dosing paradigm and revised the protocol with a major protocol amendment in March 2019 to include 3 dosing regimens under a blinded bi-monthly dosing paradigm: RO7234292 Q8W, RO7234292 every 16 weeks (Q16W) arm (with alternating placebo), and placebo Q8W.

[figure not shown]
The details of this amendment including rationale are in Protocol Version 4, and a comparison of old (Versions 1-3) and new study designs (version 4+) in [Figure 1](#).

Prior to stopping the enrollment in Protocol versions 1-3 on 29 March 2019, 108 patients were randomized in Canada, USA and Spain referred to as the "Original Design Cohort" (ODC). The ODC will not be included in the primary efficacy and safety analysis of the new study design (Protocol version 4 onwards). The Sponsor made this decision to prevent the potential bias that would have been introduced to the trial results if patients under different regimens (monthly and bi-monthly) were contained in the same analysis. Instead, ODC patients have been discontinued from Study BN40423 and offered enrollment into the long-term open label extension study (BN40955).

This Statistical Analysis Plan (SAP) will describe the statistical analysis of the ODC only. A separate SAP will be provided for the analysis of the new cohort (Protocol Version 4 onwards).

Because the study design was changed, patients in the ODC received less than two years of treatment and did not reach the Week 101 assessment. The analysis of clinical endpoints will be deemed as exploratory analysis. No formal hypothesis testing will be performed and all the p -values will be descriptive.

Figure 1 Phase III Protocol BN40423 Cohorts

Q4W= every 4 weeks; Q8W= every 8 weeks; Q16W= every 16 weeks

2. STUDY DESIGN

One hundred and eight patients were enrolled in the ODC of Study BN40423. Prospective patients went through screening assessments during a 4-week screening period.

Upon completion of the screening period, eligible patients were randomly allocated in a 1:1:1 ratio to receive 120 mg RO7234292 Q4W, 120 mg RO7234292 Q8W, or placebo Q4W by IT injection. To maintain the study blind and integrity, patients in the RO7234292 Q8W arm also receive placebo (i.e., alternating Q4W administrations of active drug and placebo).

2.1 PROTOCOL SYNOPSIS

The Protocol Synopsis is in [Appendix 1](#). For additional details, see the Schedule of Assessments in [Appendix 2](#).

2.2 OUTCOME MEASURES

2.2.1 Pharmacodynamic Endpoints

- **Biomarkers**
 - Cerebrospinal fluid (CSF) levels of –
 - mHTT
 - neurofilament light chain (NFL)
 - Chitinase-3-like protein 1 (YKL-40)
 - Tau
 - Total protein levels
 - Plasma levels of NFL
- **Neuroimaging volumes (Structural Magnetic Resonance Imaging [MRI])**
 - Baseline Caudate volume and Caudate Boundary Shift Integral (CBSI)

- Baseline Whole brain volume and whole-brain BSI (KNBBSI)
- Baseline Ventricular volume and ventricle BSI (VBSI)
- **Clinical endpoints**
 - Unified Huntington's Disease Rating Scale (cUHDRS)
 - Total Functional Capacity (TFC) scale score
 - Total Motor Score (TMS)
 - Symbol Digit Modalities Test (SDMT)
 - Stroop Word Reading Testing (SWR)
- **Digital endpoints**
 - Chorea
 - Speed tapping
 - Symbol digit modality test (SDMT)
 - Stroop Word Reading Test (SWT)
 - 2 minute walking
 - U turn
 - Balance test
 - Draw a shape

2.2.2 Pharmacokinetic Endpoints

The PK endpoints are as follows:

- Concentration of RO7234292 in plasma at all available timepoints
- Trough concentration of RO7234292 in CSF at all available timepoints

2.2.3 Immunogenicity Endpoints

The immunogenicity endpoints are as follows:

- Incidence of anti-drug antibodies (ADAs) at specified time-points relative to the prevalence of ADAs at baseline
- Titer and antibody subtype, determined if ADAs are identified

2.2.4 Safety Outcome Endpoints

Safety will be assessed on the basis of the following endpoints:

- Incidence and severity of adverse events (AEs)
- Change from baseline in Montreal Cognitive Assessment (MoCA)
- Change from baseline in vital signs
- Change from baseline in ECG parameters
- Change from baseline in clinical laboratory results including CSF findings

- Proportion of patients with suicidal ideation or behavior, as assessed by Columbia-Suicide Severity Rating Scale (C-SSRS) score at each visit, including detailed focus on any individual cases identified as having severe ideation or behavior during the study conduct

2.3 ANALYSIS TIMING

The analysis will be conducted once the last patient among the 108 patients has either withdrawn early from the study or enrolled to the BN40955 study and when all data of the 108 patients needed for the planned analysis have been made available, cleaned and verified and the database has been locked.

3. STATISTICAL METHODS

3.1 ANALYSIS POPULATIONS

3.1.1 Intent-to-Treat Population

The intent-to-treat (ITT) population will consist of all patients who were randomized and received any study treatment. Randomized patients who receive therapy different from the one assigned at randomization will be summarized in the group according to their planned randomized treatment.

The ITT population will be the primary population for all clinical efficacy endpoints, CSF biomarker and MRI analysis.

3.1.2 Safety Population

The ITT population will also be used for all analyses of safety data.

For the purpose of all safety analyses, at the time of unblinding, it will be assessed whether at any time during the course of the study, patients received a treatment different from the one they were randomized to.

For patients who were randomized to placebo but received any active treatment by error, if there is any safety signal of concern present, they will be summarized under the active treatment group; otherwise will be summarized under placebo.

The final decision on this will only be possible after unblinding.

3.1.3 Pharmacokinetic-Evaluable Population

The PK population will include all randomized patients who received at least one dose, and had sufficient sampling to permit PK evaluation.

3.1.4 Immunogenicity

The immunogenicity population will include all randomized patients who received any study treatment and with at least one post-dose ADA assessment. Patients will be grouped according to the treatment received.

3.2 ANALYSIS OF STUDY CONDUCT

The numbers of patients who enrolled in the ODC, discontinued from the treatment, and the study early and whether they roll-over or not to the BN40955 study will be summarized overall and by treatment arm. Reasons for premature study withdrawal will be listed and summarized. Enrollment and major protocol deviations will be listed and evaluated for their potential effects on the interpretation of study results. The population for the analysis of study conduct will be all randomized patients, unless stated otherwise.

3.3 BASELINE DEFINITION

The baseline will be defined as the last non-missing assessment prior to the randomization date or the first dosing date, whichever is the latest.

3.4 STUDY DAY DEFINITION

Day 1 will be defined as the randomization date or the first dosing date, whichever is the latest. Study Day will be calculated relative to the Day 1 as defined:

If the assessment date is on or after the Day 1,

$$\text{Study Day} = \text{assessment date} - \text{Day 1} + 1$$

If the assessment date is before the Day 1,

$$\text{Study Day} = \text{assessment date} - \text{Day 1}$$

3.5 ANALYSIS OF TREATMENT GROUP COMPARABILITY

Demographic and baseline characteristics will be summarized by treatment group using means, SD, medians and ranges for continuous variables and proportions for categorical variables, as appropriate. Summaries will be presented overall and by treatment.

3.6 CSF AND PLASMA BIOMARKER ANALYSES

Absolute values and change from baseline values for all biomarker assessments (as listed in Section 2.2.1) will be summarized by descriptive statistics at each visit by treatment group.

For all biomarkers, the measurement that is below the limit of quantification (BLQ), the value will be set to BLQ divided by two (BLQ / 2). A summary table for subjects who were BLQ by regimen and visit will be presented.

All biomarkers will be log-transformed in the statistical modelling and correlation analyses.

- **Analysis of Longitudinal Changes Over Time**

The mixed-effect model repeated measures (MMRM) analysis will be performed for each individual parameter including data from baseline up to 7 months. The fixed effects in the model will include the corresponding baseline value of the biomarker analyzed (with log transformation), visit (as categorical variable), treatment, treatment by visit interaction, baseline age, baseline cytosine-adenine-guanine (CAG) repeat length and CAP score (the latter defined as $CAP = [CAG - 33.66] * \text{Baseline age}$). Visit will be fitted as a repeated variable within a patient. An unstructured (UN) variance-covariance structure will be applied to model the within-patients' errors; if the model fails to converge, the following variance-covariance structures will be tested as alternatives in the pre-specified order: Heterogeneous Toeplitz (TOEPH), Antedependence (ANTE[1]) and Heterogeneous Compound Symmetry (CSH).

Least squares means (LSM) estimates based on the MMRM model, at each time-point, along with corresponding standard error, 95% CI and unadjusted p -value will be presented (back-transformation) for each regimen as well as for the comparison of each active arm against placebo.

The full list of analyses is summarized in [Table 1](#).

Technical details of the MMRM and sample SAS code are included in the [Appendix 3](#).

- **Analysis of Relationship Between Selected Parameters**

The following analyses will be conducted to describe the relationship between selected pairs of parameters:

- the association of baseline CSF mHTT with baseline CSF biomarkers (Tau, NfL, YKL-40, and total protein levels)
- the prognostic value of baseline CSF mHTT for the changes in CSF biomarkers at 3, 5 and 7 months, respectively
- the association of the changes in CSF mHTT with the changes in CSF biomarkers at 3, 5 and 7 months, respectively
- the association of baseline CSF NfL with the baseline plasma NfL
- the association of the changes in CSF NfL with the changes in plasma NfL at 3 and 5 months, respectively
- the association of baseline CSF mHTT with the baseline MRI volumes.
- the association of the changes in CSF mHTT with the BSI at 3 months
- the association of baseline CSF biomarkers with the baseline MRI volumes.
- the association of the changes in CSF biomarkers with the BSI at 3 months
- the association of the baseline CSF mHTT with the clinical endpoints at baseline

- the association of the baseline CSF biomarkers with the clinical endpoints at baseline
- the association of the baseline CSF mHTT with the change in the clinical endpoints at 3 months and 5 months, respectively
- the association of the baseline CSF biomarkers with the change in the clinical endpoints at 3 months and 5 months, respectively
- the association of the changes in CSF mHTT with the changes in the clinical endpoints at 3 months and 5 months, respectively
- the association of the changes in CSF biomarkers with the changes in the clinical endpoints at 3 months and 5 months, respectively

Both descriptive statistics (scatter plots) and model-based analyses will be applied.

Descriptive analyses - Scatter plots between selected pairs of parameters will be presented by time point and by treatment. Spearman correlation coefficients will be calculated.

Model-based analyses - In order to model the relationship between a continuous response variable (e.g. the change in CSF Tau at 3 months) and a main predictor (e.g., baseline value of mHTT), a linear regression model (LRM) will be used. The model will include treatment and treatment by main predictor interaction terms as independent variables. Age, CAG repeat length and CAP scores will be included for covariate adjustment.

The full list of analyses, together with specifications about additional covariates to account for, is provided in [Table 2](#).

A similar model, with a term for the main predictor but without any term including treatment, will also be considered to allow estimating the relationship between the response and the main predictor based on a pooled (across treatments) population.

The LSM estimates for the slope of the main predictor (X-variable in [Table 2](#)) along with corresponding standard error, 95% CI and unadjusted p -value will be presented. The estimated effect represents the effect of the main predictor on the response adjusted for all other covariates in the model. Distributional assumptions underlying the model used for analysis will be examined to gain confidence that the model assumptions are reasonable and where needed, sensitivity analyses will be performed.

Additional analyses, not listed in this SAP, may be conducted to better understand any safety concern which may arise.

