3.8 MRI ANALYSES

A 3D T1-weighted structural MRI scan will be used to quantitate whole brain, caudate and intraventricular volumes. The only absolute measures are baseline volumes, while boundary shift integral (BSI) are used to assess changes in volumes over time. Three boundary shift integrals will be considered: K-means ventricular boundary shift integral (VBSI), K-means CBSI and K-means brain boundary shift integral (KNBBSI). To be noticed is that BSI values represent already a measure of change from baseline.

Only data with a QC flag equals to 'Pass' will be used in the analysis.

Descriptive tables and plots will be performed. The relationship between the MRI at baseline and CSF mHTT at baseline will be performed using the methods as described in Section 3.4.

In addition, the analysis of covariance (ANCOVA) will be performed to compare the percentage change of BSI at 3 months between the treatment groups. The model will include baseline age, CAG repeat length, baseline CAP score and treatment as covariate. The estimated treatment difference at 3 months and corresponding 95% CIs will be presented.

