UHDRS	Y	Y	Y	Y	Y	all available	BSL 1 month, 5 months	Yes
BSI*	Y	Y		Y*	Y‡	all available	3 months	No**
BSL MRI Volume		Y	Y			all available	Screening	No
PK	Y	Y	Y			all available		No
ADA		Y	Y			all available		No

ADA= anti-drug antibody; BSI= Boundary Shift Integral; BSL=Baseline; CSF= cerebrospinal fluid; MRI= magnetic resonance imaging; MMRM= mixed-model repeated measures; mHTT= mutant huntingtin (protein); NFL= neurofilament light chain (protein); PK= pharmacokinetic; UHDRS= Unified Huntington's Disease Rating Scale; Y= Yes.

Absolute=measured data at a given time point.

Change (%Change)= change from baseline from a given post-baseline measurement (expressed as a percentage)

*BSI is already a measure of change in volume (thus the change is not derived as for the other variables)

‡ %-Change for BSI is derived as $\left(\frac{BSI}{baseline\ volume}\right) \cdot 100$

** ANCOVA will be applied to compare the percentage of change of BSI at 3 months between the treatment groups.

Table 2 Overview of Planned Outputs to Describe the Association Between Selected Pairs of Parameters

Paired Variables	Data Type				Time points**	Additional covariates in statistical models
	X-variable		Y-variable			
	Absolute	Change	Absolute	Change		
X=mHTT, Y= CSF Biomarkers (NFL, YKL-40 Tau Total Protein)	Y		Y		X and Y=BSL	BSL Age, CAG, CAP
	Y			Y	X=BSL, Y=3M, 5M, 7M	BSL Age, CAG, CAP BSL CSF BM
		Y		Y	X and Y=3M, 5M, 7M	BSL Age, CAG, CAP BSL CSF BM, BSL mHTT
X= CSF Biomarkers (mHTT, NFL, YKL-40 Tau, and CSF total protein) Y=Clinical endpoints (cUHDRS, TFC, TMS, SDMT, and SWR)	Y		Y		X and Y=BSL	BSL Age, CAG, CAP, Region
	Y			Y	X=BSL, Y=5M	BSL Age, CAG, CAP, Region BSL ClinEP
		Y		Y	X=3M, 5M, Y=5M	BSL Age, CAG, CAP, Region BSL ClinEP, BSL CSF BM
X=CSF-Nfl, Y=Plasma-Nfl	Y		Y		X and Y=BSL	NA
		Y		Y	X and Y=3M,5M	NA
X=mHTT, Y=MRI	Y		Y		X and Y=BSL	BSL Age, CAG, CAP

BM=biomarker; BSL=baseline; ClinEP=clinical endpoints; Change = Change from baseline; CSF= cerebrospinal fluid; MRI= magnetic resonance imaging; mHTT= mutant huntingtin (protein); NA=not applicable; NFL= neurofilament light chain (protein).

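### SAP Version 1 relates baseline CSF markers to baseline brain volumes adjusting only for age, CAG and CAP; leaving out sex and head size probably costs precision

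*SAP*

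**What the plan says.** Section 3.6 of SAP Version 1 lists pairs of parameters whose relationship is to be described. Two pairs concern baseline imaging: "the association of baseline CSF mHTT with the baseline MRI volumes" and "the association of baseline CSF biomarkers with the baseline MRI volumes". Each is examined with scatter plots, Spearman coefficients and a linear regression. The regression contains the marker, treatment and their interaction; a second version drops the treatment terms and pools the arms. On adjustment it states: "Age, CAG repeat length and CAP scores will be included for covariate adjustment".

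Section 3.6 then says "The full list of analyses, together with specifications about additional covariates to account for, is provided in" Table 2. The Table 2 row for mHTT against MRI takes both variables as absolute values at baseline and gives the covariates as "BSL Age, CAG, CAP". The table as it can be read has no row for the other CSF biomarkers against MRI volumes, so for those only the general sentence in Section 3.6 applies.

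On the scale of the volumes, Section 3.8 says "The only absolute measures are baseline volumes, while boundary shift integral (BSI) are used to assess changes in volumes over time". The notes to Table 1 explain the column label: "Absolute=measured data at a given time point". SAP Version 1 mentions neither sex, head size nor intracranial volume in its MRI or association methods. Section 3.8 also repeats the mHTT analysis but refers to Section 3.4 for its method. Section 3.4 defines study day, so Section 3.6 is presumably meant.

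**The concern.** A measured brain volume reflects how large the head is as well as how much tissue has been lost, and only the second bears on the disease. That is a general anatomical premise; the documents do not discuss it. Age, CAG and CAP describe disease burden. CAP is computed from the other two, so the covariate set contains no variable for body or head size.

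Patient-to-patient variation in size therefore goes into the residual. The slope of volume on the marker is then estimated less precisely than the data allow, and a real association is harder to see. A second consequence is possible but conditional: if the CSF concentration also differs by sex or head size, part of the slope would reflect size and not atrophy.

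The covariate set is not left open. Section 3.6 names Table 2 as the place for additional covariates, and the MRI row adds none. Elsewhere the plan does suit the covariates to the outcome: region is added for clinical endpoints, and baseline values for the models of change.

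**Working it through.** The plan gives no power or precision figure for these associations, so there is none to reproduce. What follows is illustration on stated assumptions.

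**Inputs**
- n = 108, the number enrolled (SAP Version 1, Section 2). This is an upper bound, because Section 3.8 admits only scans that pass quality control.
- Pooled model: intercept, marker, age, CAG, CAP = 5 parameters, so 108 − 5 = 103 residual degrees of freedom. With sex and head size added: 101.
- R² = share of the volume variance left by the planned model that sex and head size explain. Assumed 0.20 to 0.70.
- c = correlation of sex or head size with the CSF marker. Assumed 0 unless stated.

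**Precision**

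The ratio of the slope's standard error after to before adjustment is √(1 − R²), and the equivalent sample size is 108/(1 − R²).

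| R² | SE ratio | SE falls by | Equivalent n |
|---|---|---|---|
| 0.20 | √0.80 = 0.894 | 11% | 135 |
| 0.50 | √0.50 = 0.707 | 29% | 216 |
| 0.70 | √0.30 = 0.548 | 45% | 360 |

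The two extra parameters cost a factor √(103/101) = 1.010, so the ratios become 0.903, 0.714 and 0.553. On the estimated residual variance the two covariates pay for themselves once R² exceeds 2/103, about 2%. If they are correlated with the marker, the standard error is also multiplied by 1/√(1 − c²), which is 1.02 at c = 0.2.

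**What this does to detection**

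Fix the correlation r given all covariates, including sex and head size. With c = 0 the planned model sees r√(1 − R²). Approximate power at two-sided 5% is Φ(atanh(r)·√(n − 3 − k) − 1.96), where k is the number of covariates: 3 as planned, 5 after the change.

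| r | With sex and head size | As planned, R² = 0.20 | 0.50 | 0.70 |
|---|---|---|---|---|
| 0.20 | 0.53 | 0.45 | 0.30 | 0.20 |
| 0.30 | 0.87 | 0.79 | 0.59 | 0.39 |

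Example: r = 0.30 and R² = 0.50 give 0.30 × 0.707 = 0.212; atanh(0.212) × √102 = 2.18; Φ(2.18 − 1.96) = 0.59. With fewer usable scans all the values fall: at n = 80 and r = 0.30, power is 0.75 with the covariates and 0.46 without (R² = 0.50).

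**Bias, only if the marker is related to size**

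With no true association, the planned model would show a correlation of c√R².
- c = 0: correlation 0, and the 5% rejection rate is unchanged.
- c = 0.2, R² = 0.10: 0.2 × 0.316 = 0.06, rejection rate 0.10.
- c = 0.2, R² = 0.50: 0.2 × 0.707 = 0.14, rejection rate 0.30.

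The documents give no value for c.

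**The case against.** The plan states nothing false or contradictory here. Section 1 of SAP Version 1 makes the clinical analyses exploratory, rules out formal testing and calls all p-values descriptive. The two associations belong to a long list, in a cohort kept out of the primary efficacy and safety analysis. All of this stands, and it limits the weight of the point.

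The word absolute should not be pressed. In "The only absolute measures are baseline volumes" and in the table notes it separates a measured value from a change. It does not say that volumes are uncorrected for head size, and a normalisation step in an imaging document not at hand cannot be excluded. What can be said is that this plan states none.

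A reader might go further in three ways that the documents do not support:
- That the association will be distorted. This needs a link between the CSF marker and sex or head size, and nothing in the plan shows one.
- That the plan contradicts itself because BSI is divided by baseline volume. That division turns a change into a percentage change; it is not a head-size correction withheld elsewhere.
- That power would rise from 0.53 to 0.62, 0.81 or 0.95 (R² of 0.20, 0.50, 0.70). Those values arise only if 0.20 is the correlation before adjustment. If it is the fully adjusted value, power is 0.53 after the change.

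Nor can the full precision gain and the bias be claimed together: the first assumes the covariates unrelated to the marker, the second assumes they are related.

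**Conclusion.** The point holds as a probable loss of precision. The baseline-volume models are fixed with age, CAG and CAP as the only patient characteristics, and variation in volume due to sex and head size is left in the residual. On the assumption that these explain 20% to 70% of the remaining variance and are unrelated to the marker, the standard error of the slope is higher than it need be, and adjustment would lower it by about 11% to 45%. One range has been used for whole brain, caudate and ventricles, although the share may well differ among them. The analysable number is at most 108. Bias remains a possibility that the documents neither show nor rule out. No treatment comparison, endpoint or sample size depends on these analyses, so the importance is low.

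**What to change.** - Add sex as a covariate in every SAP Version 1 model with baseline MRI volume as outcome. Demographic data are collected at screening, and the Version 3 plan already uses sex as a subgroup variable.
- Where intracranial volume is available or can be derived from the same T1 scan, add it as a covariate too, or analyse volume as a fraction of it while keeping sex in the model. If the volumes supplied are already normalised, say so and add sex only.
- Amend the mHTT/MRI row of Table 2, and state that the same covariates apply to the other CSF biomarkers. Report Spearman coefficients as partial correlations on the same set beside the unadjusted ones.
- Correct the reference in Section 3.8 to Section 3.4 at the same time.

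Sex costs a line of wording and one degree of freedom. Intracranial volume costs a second degree of freedom and one further image-derived measure, which may need its own segmentation and quality check. If that is not practicable, adding sex alone is still worthwhile.
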